WEL-SF Weight Efficacy Lifestyle questionnaire – Short Form

1. ABSTRACT

BACKGROUND

Prolonged adult obesity is a consistent predictor of major chronic disease risk, including diabetes, heart disease, stroke, and hormone-related cancers. The traditional government-recommended approach to weight loss for obese patients has been calorie-counting / portion control (CC). In 2011 the government began recommending the MyPlate approach (MyP). The CC condition asks overweight patients to reduce their daily calorie intake to less than a recommended calorie target. The MyP approach also limits daily calories but emphasizes eating MORE high-satiety/ high-satiety foods by making ½ of daily food choices minimally processed fruits and vegetables, and ¼ of daily food choices whole grains. The relative effectiveness of the MyP approach compared to the CC approach has not been clinically tested to date in urban, low-income populations.

OBJECTIVES

We propose a randomized controlled trial comparing the patient-centeredness and efficacy of the CC and MyP approaches. MyP uses progressive goal-setting to facilitate a doubling of usual fruit and vegetable intake. To facilitate adherence, both approaches also include changes in the home environment to make healthier choices easier choices. Both conditions encourage patients to do 150 minutes of moderate to vigorous physical activity a week.

Specific Aims

Aim #1. Use qualitative information from patients and clinicians to revise proposed intervention materials and procedures.

Aim #2. Use results of a pilot test of the intervention conditions to revise intervention materials and procedures.

Aim #3. Conduct a 12-months randomized controlled trial involving two home visits, two group education classes, and 7 telephone support/ lifestyle change coaching calls in both conditions.

Aim #4. Obtain qualitative data from providers and coaches; combine with patient survey data to assess intervention feasibility, acceptability and perceived usefulness.

Aim #5. Disseminate results and recommendations to stakeholder groups.

METHODS

Study participants are 261 overweight or obese patients with a BMI range of 27.0-40.3, low-income, mostly Latino and African American adult patients attending community health centers in Long Beach, California. The MyP and CC interventions will be implemented by trained community lifestyle change coaches (promotoras) with brief support from clinicians.

Primary hypotheses: Compared to the CC approach, the MyP approach will yield better 12 months outcomes in terms of lower levels of everyday hunger, higher meal satisfaction, higher patient quality of life, higher patient self-efficacy at adhering to federal nutrition and physical activity recommendations, higher patient weight loss self-efficacy, and higher patient satisfaction with the weight loss program. **Secondary hypotheses:** Both intervention conditions will yield significant and similar declines in body weight and waist circumference; the MyP condition will yield greater reduction in systolic blood pressure than the CC condition.

PATIENT OUTCOMES (PROJECTED)

Patient-centered outcomes include: level of everyday hunger, health-related quality of life, self-efficacy to eat more fruits and vegetables as recommended on choosemyplate.gov, and patient satisfaction with the weight loss program, all of which are expected to favor the MyP condition at 12 months follow-up relative to the CC condition. Medical outcomes include changes in body

weight, waist circumference, and blood pressure. Body composition was expected to improve in both conditions but systolic blood pressure reduction was expected only in the MyP condition.

2. SPECIFIC AIMS

We propose a randomized controlled trial (RCT) comparing the patient-centeredness and efficacy of two government-supported lifestyle change approaches to reducing patient obesity risk. Study participants are 261 obese, low income, mostly Latino and African American adult patients or staff associated with community health centers in Long Beach, California. The interventions will be implemented by trained community lifestyle change coaches (promotoras) with brief support from clinicians.

The first weight loss approach is the calorie-counting (CC), portion-cutting approach recommended at www.nutrition.gov. The second is the fill-up-sooner-on-fewer-calories approach found at www.choosemyplate.gov (MyP). The CC condition asks overweight patients to reduce their daily calorie intake to less than a recommended calorie target. The MyP approach also limits daily calories but emphasizes eating MORE high-satiety/ high-satiety foods by making ½ of daily food choices fruits and vegetables, and ¼ of daily food choices whole grains. MyP uses ipsative, progressive goal-setting to facilitate a doubling of usual fruit and vegetable intake. To facilitate adherence, the MyP approach also includes home environment changes to make healthier choices easier choices. All conditions encourage doing at least 150 minutes of moderate to vigorous physical activity a week.

Primary patient-centered outcomes include levels of everyday hunger, meal satisfaction, health-related quality of life, self-efficacy to eat more fruits and vegetables as recommended on choosemyplate.gov, and patient satisfaction with the weight loss program, all of which are expected to favor the MyP condition at 12 months follow-up relative to the CC condition. The primary medical outcomes are a reduction in body weight and waist circumference

Specific Aims

Aim #1. Use qualitative information from patients and clinical staff to revise intervention materials and procedures.

Aim #2. Use results of a pilot test of the intervention conditions to revise intervention materials and procedures.

Aim #3. Conduct a 12-months RCT involving two home visits, two group education classes, and seven telephone support/ lifestyle change coaching calls.

Aim #4. Obtain qualitative data from providers and coaches; combine with participant data to assess intervention feasibility, acceptability and perceived usefulness.

Aim #5. Disseminate results and recommendations to community groups and public health professionals.

Primary patient-centered hypotheses: Compared to the CC approach, the MyP approach will yield better 12-months outcomes in terms of reduced everyday hunger, increased meal satisfaction, increased participant quality of life, increased participant self-efficacy to eat more fruits and vegetables, and participant satisfaction with the weight control program. Primary medical hypotheses: Both government-recommended conditions will yield significant and similar 12-months declines in body weight. The MyP condition will reduce systolic blood pressure more than the CC condition.

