13. STATISTICAL POWER AND SAMPLE SIZE ESTIMATION

Hypotheses for the Two-Group Randomized Control Trial Design: The aim is to conduct an RCT of the impact of CC versus MyP on patient-centered outcomes in up to eight community clinic sites in Long Beach. Participants will include: 150 patients randomly assigned to receive

Patterned after protocol published online in association with Appel et al. (2011)¹⁵

CC from trained health coaches, another 150 patients assigned to receive MyP from another group of trained health coaches over the course of 12 sessions in six months.

Intervention check: Does exposure to MyP versus CC lead to increased patient reports of fruit and vegetable intake in MyP? A preliminary check will be made to confirm that one of the defining features of the MyP approach, namely a doubling of F&V intake, was reflected in study participants' daily intake of F&V assessed at follow-up. If no difference were observed in F&V assessed at follow-up then the validity of the experimental contrast would be jeopardized. There could still be experimental effects, but the causal mechanisms would be unknown. Because numerous studies have succeeded in getting patients to double their intake of F&V for up to four years, a negative outcome of this intervention check is unlikely.²⁵

Question: Does exposure to MyP versus CC lead to decreased patient 12-months reports of daily hunger ratings/ daily meal satisfaction ratings/ daily fullness ratings in MyP during a time when patients were trying to lose excess weight (primary)? Will exposure to MyP versus CC lead to increased patient weight control self-efficacy, patient quality of life and patient satisfaction with her/his weight control program (primary)?

Question: Will exposure to MyP versus CC lead to increased weight loss/ reduced waist circumference equally for both conditions sustained for 12 months (secondary)?

Avoidance of bias. Covariates and effect modifiers. Standard demographic variables, including gender, age, ethnicity, marital status, and educational attainment will be included as covariates. Possible effect modifiers will also be included as covariates, including language preference (English / Spanish), last month food security, meal-skipping status, and daily physical activity level.

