Sample size. (3) Statistical power. We power this proposal for the two-group (MyP vs CC) randomized design, setting alpha at 0.025 in order to have an experiment wise type I error rate of 0.05 after testing two hypotheses. Test of hypothesis #1 is therefore a test of the effect of MyP versus CC on the 12 months report of freedom from hunger measure used in the trial most similar to the trial proposed here.¹⁸³ The intervention effect size reported by Ello-Martin and associates is Cohen's $d = .52$. (Cohen's Effect Size = $(53.5 - 46.7) / 13.2 = .52$). The total sample sized needed to detect this effect, given a two-tailed critical $P = .025$, minimum statistical power of .80, and $\rho = .85$ the total sample size needed is approximately $N = 144$. The test of the second hypothesis is a test of MyP versus CC on the body weight lost over 12 months. We have three sources to draw on for estimating effect size involving weight loss over 12 months. The first is Ello-Martin and associates, whose low-fat, high fruit and vegetables intervention²⁰ was similar to but not identical to the DASH diet + (sat. fat & sugar restriction) featured in the current proposal.¹⁶ Ello-Martin's DASH-similar + fat restricted diet yielded a 12-months weight loss of 7.9 kg (SE=0.9, n=35) whereas the fat restriction-only condition yielded a 12-months weight loss of 6.4 kg (SE = 0.9, n=36). The total sample size needed to detect a similar 12-months weight loss difference at $\alpha=0.025$, $\text{power}=0.80$, $\rho = .7$ is $N= 206$ ($n=103$ per group). In Appel's recent clinical trial¹⁵ the in-person DASH-like dietary intervention yielded a 5.4 kg (SE=0.7, n=124) weight loss relative to baseline at 12 months follow-up.¹⁵ The body weight lost in response to Wadden's DPP-like dietary intervention¹⁴ was 3.4 kg (SE=0.6, n = 112) at 12 months follow-up¹⁸⁴ By design the protocols followed by Appel et al. (2011) and by Wadden et al. (2011) were similar, so comparing means across these two studies is informative. The sample size needed to detect this difference at 12 months at $\alpha = 0.025$, $\text{power}=0.80$, $\rho = .7$ is $N = 270$ ($n = 135$ per group). Based on the best available sources in the literature for information about reasonable estimates of the effect size to be expected and given an expected attrition of 20% at 6 month follow-up, the baseline initial sample of 300 (N=300 for 2 groups) appears to provide ample statistical power for the two experimental comparison hypotheses

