
Patterned after protocol published online in association with Appel et al. (2011)¹⁵

considered primary in this proposal. For a substudy involving only the 76% of participants who are Latino, the sample size (N =228) also yields acceptable statistical power. All additional hypothesis-testing will involve secondary hypotheses.

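### The plan hypothesises similar weight loss in the two arms but sizes and tests a difference, with no margin or interval rule by which similarity could be concluded

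*Combined protocol and SAP*

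**What the plan says.** Three places predict that the arms will lose about the same weight.

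- Section 2 (Specific Aims), labelled a primary medical hypothesis: "Both government-recommended conditions will yield significant and similar 12-months declines in body weight".
- Section 1 (Abstract), labelled secondary: "Both intervention conditions will yield significant and similar declines in body weight and waist circumference".
- Section 13, labelled secondary: "Will exposure to MyP versus CC lead to increased weight loss/ reduced waist circumference equally for both conditions sustained for 12 months (secondary".

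The sample-size text in section 13 then defines the comparison differently: "The test of the second hypothesis is a test of MyP versus CC on the body weight lost over 12 months". The first calculation is introduced as "The total sample size needed to detect a similar 12-months weight loss difference", using 7.9 against 6.4 kg from a year-long trial of two weight-loss diets. The second uses 5.4 kg from a DASH-like arm in one trial and 3.4 kg from a DPP-like arm in another. The section describes such inputs as "reasonable estimates of the effect size to be expected". It assigns alpha 0.025 to each of two hypotheses, which it calls "considered primary in this proposal".

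Section 14 plans mixed-model contrasts, missing-data sensitivity analyses, intention-to-treat and on-treatment comparisons. It contains no equivalence margin, no confidence-interval criterion and no other rule for concluding that the arms are similar.

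**The concern.** A difference test can produce evidence against equality. If it fails to do so, that is not evidence of similarity, because an imprecise estimate gives the same result. As written, the plan expects similarity in its hypotheses and a difference of 1.5 to 2.0 kg in its sample size, and a reader cannot tell which one the weight result is meant to test.

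This bears on the trial's main message. Section 4 asks which approach clinics should feature. If hunger favours MyP and the weight test is non-significant, the natural summary is less hunger for the same weight loss. The plan supplies no criterion for the second half of that sentence. In addition, one option in section 14 assumes zero change for missing 12-month weights; applied in both arms, it would tend to shrink a real difference.

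**Working it through.** **Inputs.** All are from section 13, except the reduced sample of 261, which is in section 4.

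- First source: SE 0.9 (n = 35) and SE 0.9 (n = 36); difference 7.9 − 6.4 = 1.5 kg.
- Second source: SE 0.7 (n = 124) and SE 0.6 (n = 112); difference 5.4 − 3.4 = 2.0 kg.
- Alpha 0.025, power 0.80, rho 0.7. A two-tailed test is stated for hunger only.
- Attrition: "given an expected attrition of 20% at 6 month follow-up".

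**Step 1: implied SDs (SE × √n).** First source: 0.9√35 = 5.32 and 0.9√36 = 5.40, root mean square 5.36 kg. Second source: 0.7√124 = 7.79 and 0.6√112 = 6.35, root mean square 7.11 kg.

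**Step 2: the plan's own sample sizes.** Per arm, n = 2 × SD² × (1 − rho²) × (z_alpha + 0.842)² / d², with 1 − 0.49 = 0.51.

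- 1.5 kg, z = 1.96: 2 × 5.36² × 0.51 × 7.85 / 2.25 gives 103 per arm, the stated 206. This z is one-sided 0.025 (or two-sided 0.05). At two-sided 0.025 (z = 2.241) it is 124 per arm, 248 in total.
- 2.0 kg, same method: 102 per arm (204) at z = 1.96, or 123 per arm (246) at z = 2.241. The stated 270 is not reproduced.

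Both figures are sample sizes for detecting a difference; neither calculation contains a margin.

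**Step 3: what a non-significant result would leave open.** SE of the difference = SD × √(4/N), multiplied by √0.51 = 0.714 if rho is applied as a baseline adjustment. The source SEs are already for weight loss, so applying rho may double count; both readings are shown. The largest non-significant difference at two-sided 0.025 is 2.241 × SE, and its upper 95% limit is (2.241 + 1.96) × SE.

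| N = 261 | SD 5.36, rho | SD 7.11, rho | SD 5.36, no rho | SD 7.11, no rho |
|---|---|---|---|---|
| SE (kg) | 0.474 | 0.629 | 0.664 | 0.880 |
| Largest non-significant difference (kg) | 1.06 | 1.41 | 1.49 | 1.97 |
| Upper 95% limit (kg) | 1.99 | 2.64 | 2.79 | 3.70 |

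If the 20% attrition stated for 6 months is assumed to hold at 12 months, about 209 are evaluable. The ranges become 1.2 to 2.2 kg, with upper limits of 2.2 to 4.1 kg. At one-sided 0.025 and N = 261 they are 0.9 to 1.7 kg and 1.9 to 3.5 kg.

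**Step 4: reading.** In every column a result could be non-significant while its interval still included the 1.5 kg difference of the first source, and in three of the four the 2.0 kg of the second. In the first column the limit, 1.99 kg, falls just short of 2.0 kg.

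**The case against.** The hypothesis has two parts, and a reader might infer that no result could confirm any of it. That goes too far. The *significant* part can be judged from within-arm change in the longitudinal mixed model, although the plan does not spell that test out. A contrast also yields an estimate and a CI, and a narrow interval near zero would inform similarity. What is missing is a threshold fixed in advance.

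A reader might also infer that the sponsor will treat a non-significant test as proof of similarity. The documents do not say so. Nor do they offer 1.5 or 2.0 kg as margins; those are expected effects.

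A third tempting reading is that the trial is badly underpowered for weight. Without rho, at two-sided 0.025 and N = 261, a true difference of the source size would be missed in about 49% of trials. But section 13 states rho = 0.7 for weight, and the 206 reproduces only with it and z = 1.96. On that basis the miss rate is 11% at 261 and 19% at 209, in line with the planned 20% or better. The point here is logical and does not rest on low power.

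Finally, *similar* may be loose wording and the difference test the real intent. That is possible. No equivalence analysis would then be missing, but the wording still contradicts the test and needs correcting.

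**Conclusion.** The point holds for the *similar* (or *equal*) component of the weight hypothesis. Sections 1, 2 and 13 predict similarity; the sample-size text in section 13 expects and tests a difference; section 14 gives no rule connecting the two. Followed exactly, the plan can produce evidence against equal weight loss but cannot establish similarity.

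The size of the gap is illustrative. It rests on back-calculated SDs, a normal approximation, equal arms, and either reading of rho. With 261 evaluable and two-sided 0.025, an observed difference of up to 1.1 to 2.0 kg would be non-significant, with a 95% CI extending to 2.0 to 3.7 kg. The logical conclusion depends on none of these figures. The hunger comparison has its own difference hypothesis and is unaffected. This should be fixed, but it does not undermine the trial's design.

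**What to change.** **Preferred.** Restate the weight hypothesis as a two-sided between-arm difference. Remove *similar* and *equally* from the Abstract, section 2 and the section 13 question; waist circumference shares two of those sentences and should be reworded with them. Report the MyP minus CC difference in 12-month weight change with its CI, and state that a non-significant result will not be read as similarity.

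**Alternative, only if the arms have not yet been compared.** Keep *similar*, but conclude it only if the whole CI lies inside a margin that the sponsor justifies clinically; otherwise report the result as inconclusive on similarity. State the CI level so that it matches the alpha given to weight. The documents do not say whether the arms have been compared, but footnote 1 in section 4 already describes the recruited sample and reference 88 was accessed in July 2017. If the comparison has been made, any such margin must be labelled post hoc.

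**With either.** State once whether weight is primary or secondary, because that sets its alpha. Section 2, the primary medical outcome paragraph in section 8 and the sample-size text treat it as primary. The Abstract and the section 13 question treat the weight hypothesis as secondary. The choice-of-outcomes paragraph in section 8 lists weight as both.

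**Cost.** Wording only; no new data or participants. The preferred option gives up the similarity claim. The alternative may leave it inconclusive. For purely illustrative margins of 1.5 to 2.0 kg, a 95% CI and zero true difference, 80% power needs N = 4 × SD² × (1.96 + 1.2816)² / margin². That is about 302 to 944 evaluable without rho, or 154 to 482 when SD² is multiplied by 0.51.

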3. BACKGROUND

Part A: Background and Significance

Impact of the Condition on the Health of Individuals and Populations (PCORI Criterion 1) Public Health and Clinical Burden of Obesity, Especially Among Low-Income Urban Latinos and African Americans.

U.S. overweight and obesity prevalence have increased greatly over the past 30 years.¹ Approximately one third of adults are overweight (BMI between 25 and 29.9 kg/m²) and another one third are obese (BMI > 30 kg/m²).¹ Low-income urban Latinos appear to be at especially high risk.² The lifetime medical cost burden of overweight and obesity is substantial and could be reduced through early treatment and prevention.³ Through a variety of mechanisms, obesity increases the risk of CVD. These include effects mediated through traditional CVD risk factors and effects that are independent of established risk factors. Specifically, in addition to increasing BP, excess body weight increases low density lipoprotein cholesterol (LDL-C), triglyceride levels, and blood glucose levels and reduces high density lipoprotein cholesterol (HDL-C) levels. As reviewed by Rashid⁴ and as recently documented by Yan,⁵ overweight and obesity have additional impact on CVD outcomes independent of their strong associations with established risk factors. The most recent American Heart Association statement recommends weight loss and regular physical activity for the prevention and treatment of obesity-related cardiovascular disease.⁶ Numerous professional organizations recommend weight loss as an integral component of CVD risk factor management, often as first-line therapy prior to the initiation of medications.⁷⁻⁹

Similarly, overweight and obesity increase the risk of type 2 diabetes, especially in ethnic minority groups.¹⁰ Lifestyle change efforts promoting weight loss in obese patients through increased physical activity and healthier food choices can reduce risk of type 2 diabetes.¹¹ About 23.6 million people in the United States have diabetes.¹² Of those, 17.9 million are diagnosed and 5.7 million are undiagnosed. Ninety to 95 percent of people with diabetes have type 2 diabetes. Diabetes is the main cause of kidney failure, limb amputation, and new-onset blindness in American adults. People with diabetes are more likely than people without diabetes to develop and die from diseases of the heart and blood vessels, that is, cardiovascular disease. Adults with diabetes have heart disease death rates about two to four times higher than adults without diabetes, and the risk for stroke is two to four times higher among people with diabetes.¹² Latinos and African Americans are particularly at risk of having type 2 diabetes.¹⁰

The decision by the American Medical Association¹³ to designate obesity as a disease has increased interest in practical, effective clinical approaches to reducing patients' obesity risk long before obesity-related biomarkers indicate proximal risk of diabetes or heart disease.

Innovation and Potential for Improvement through Research (PCORI Criterion 2)

Two rigorously designed trials of behavioral change weight loss interventions administered to patients recruited from community health clinics were reported in the New England Journal of Medicine.^{14,15} Their contrasting findings with respect to the long-term weight control benefits of lifestyle change alone were noteworthy and merited further exploring, in part because the different approaches may be associated with different patient quality of life outcomes. Both trials included an experimental arm that featured a lifestyle change intervention with no adjunctive medical assistance, adjuncts such as meal replacement products or use of pharmaceutical products approved for use as weight loss drugs. One of these lifestyle interventions featured a conventional energy restriction approach to weight loss but also featured the DASH diet,¹⁶⁻¹⁸ a model dietary pattern that all healthy American adults are encouraged to consume, regardless of weight status.¹⁹ The other lifestyle intervention was patterned after the behavioral intervention used in the Diabetes Prevention Program (DPP).¹¹

The DPP lifestyle change approach seeks to create a calorie deficit in overweight patients by increasing energy expenditure in daily physical activity and simultaneously limiting daily intake of calories. This approach had yielded 7% weight loss over 2.8 years on average and a 58% reduction in risk of diabetes compared to usual care.¹¹ In the present instance, however, the DASH-like diet yielded a 5.4 kg weight loss at 1 year whereas the DPP-like intervention yielded a 3.4 kg weight loss at 1 year. This difference mirrored the results of a 1-year trial where a fruit and vegetable-supplemented fat-restricted diet yielded better 1-year weight loss than a standard fat-restrictive weight loss regimen.²⁰ The satiation/satiety/weight control benefits of encouraging obese clinic patients to eat more fruits and vegetables was also corroborated by a clinical trial in which Weight Watchers bested a variety of clinic-provided programs.²¹ The Weight Watchers program a decade ago replaced its previous portion-controlled, calorie-counting approach with an approach encouraging increased consumption of high-satiation/ high-satiety foods, especially fruits and vegetables.^{22,23}

Although both lifestyle change approaches recommended energy restriction, the DASH-diet investigators¹⁵ focused more of their lifestyle change efforts on increasing patients' adherence to the DASH dietary pattern. A defining feature of the DASH dietary pattern is that it encourages daily intake of twice the quantity of fruits and vegetables as is typically consumed in the usual American diet. This feature has recently been given more prominence as one of the seven dietary recommendations associated with www.MyPlate.gov, the federal initiative designed to replace the food pyramid with a food plate as the nation's leading nutrition education icon. (www.MyPlate.gov) The specific recommendation is for Americans to fill half their plate with minimally processed fruits and vegetables (fruit juice is highly processed and therefore not included). The naive observer might question the wisdom of Americans doubling their consumption of any food groups, given their documentably high prevalence of obesity. Counterintuitively, interventions that induce overweight individuals to eat substantially more minimally processed fruits and vegetables than usual are consistently (but not always) associated with reduced body weight at 6-months,¹⁶ 12-months²⁰, 2-years follow-up²⁴ and 4-years follow-up.²⁵ One exception was a fruit and vegetable intervention involving breast cancer survivors.²⁶ A noteworthy difference between the previous fruit and vegetable interventions and this last one, however, is that this last one featured 12 fluid ounces of fruit/vegetable juice a day as a replacement for three servings of whole fruit or whole vegetable. The metabolic consequences of consuming carrots in the form of juice are quite different from the metabolic consequences of consuming minimally processed, whole carrots.²⁷ In general, calories consumed in liquid form have less satiety value than calories consumed in solid form.²⁸ More specifically, the conversion of whole fruit to fruit juice usually entails removal of dietary fiber.²⁹ If consumed, dietary fiber from fruit can serve as substrate for butyrate-generating or acetate-generating commensal microbes in the large bowel, which in turn can stimulate satiety-signaling via increased expression of the satiety hormones glucagon-like peptide-1 (GLP-1) or peptide tyrosine tyrosine (PYY).³⁰ Chronically depriving commensal gut microbes of dietary fiber substrate by consuming fruit in the form of juice instead of as whole fruit can contribute to gut dysbiosis, inflammation, insulin resistance, reduced satiety-signaling and eventually, obesity.³¹

While both the DPP and DASH dietary approaches have been shown to reduce excess body weight in the short run, the ability of patients to maintain these approaches for the long-term remains to be determined. Several steps were taken to ensure that the intervention effects for the MyP condition would be long-lasting.

Additional steps incorporated in the current proposal to ensure sustainable intervention impact.

We will take several steps to ensure that the intervention effects for the MyP condition would be sustainable by the community clinics. One step is to replace the masters or doctoral-level health

Patterned after protocol published online in association with Appel et al. (2011)¹⁵

educators/counselors typically used in behavioral weight loss interventions³² with trained community health workers (promotoras). The social modeling of Social Cognitive Theory^{33,34} and experience³⁵ suggest that the predominantly low income Latino immigrant patient population comprising the study population can relate to non-college-educated Latino community health workers better than they can to bilingual but non-Latino masters or doctoral-level counselors.³⁵ African American type 2 diabetes patients as well as Latino patients have benefited from use of community health workers as behavior change agents.^{36,37} On the other hand, community health workers need substantially more training and supervision to carry out the intervention according to protocol. Substantial time is devoted in Year 1 of the present proposal to the training of the community health workers. The Intervention Director's primary responsibility during the active intervention phase is to supervise the community workers in the MyP condition weekly, monitor their lifestyle coaching, and provide guidance as needed to ensure adherence to the MyPlate.gov messages. TCC nutritionists will supervise the community health workers weekly in the CC condition to ensure good adherence to the CC intervention protocol. The use of coaches with closer community ties to the participants holds promise for more sustained lifestyle behavior change benefit.^{36,38-40}

A second step was to increase the number of coaching sessions so that the maximum number of contacts was 11 contacts (2 in-home, 2 group education sessions, 7 telephone coaching sessions), to more closely approximate the number of contacts used in previous clinic-originated weight loss efforts,^{14,15,40-44} to allow for more opportunities for participant-coach problem-solving and participant trialing of specific lifestyle change strategies, and to capitalize on the motivational benefits of continued monitoring by health care professionals.⁴⁵ For this study, the health sessions were delivered in the order give below, in Table 2.

Table 2. Chronological Order and Type of Intervention Session

- | |
|--|
| 1) In-home health education session #1 |
| 2) Telephone coaching session #1 |
| 3) Group education session #1 |
| 4) Telephone coaching session #2 |
| 5) Telephone coaching session #3 |
| 6) Telephone coaching session #4 |
| 7) In-home health education session #2 |
| 8) Telephone coaching session #5 |
| 9) Group education session #2 |
| 10) Telephone coaching session #6 |
| 11) Telephone coaching session #7 |

Although patients were encouraged to complete health education sessions in this order, they were allowed to complete the lessons in the order that best fit their schedules. In addition, patients were encouraged to complete health education sessions within a 3 months period after enrollment; however, they were allowed to complete as many lessons as possible before their 6 months follow-up assessment.

A third step was to devote more intervention resources to ensuring that the participant's home environment is optimally supportive of healthier lifestyle choices. Two thirds of calories are typically consumed in the home.⁴⁶ There is increasing evidence that, if not addressed, the visual cues in the typical home environment can undermine individual efforts to adopt healthier lifestyle behaviors and can contribute to relapse despite the strongest behavioral modification

Patterned after protocol published online in association with Appel et al. (2011)¹⁵

efforts.⁴⁶ Both physical (e.g., type of food available) and social (e.g., support from family) factors in this setting have been associated with weight, dietary habits, and activity patterns.^{47,48} Demonstrated links between the physical home environment and behavior include relationships between available high-fat foods and fat intake,⁴⁹ access to home exercise equipment and activity levels,^{50,51} and number of TV sets and amount of television viewing.⁵² In the most ambitious home environment-focused weight loss intervention published to date,⁴⁶ researchers used checklists to get participants to rid the home of high-calorie, high-fat foods and to stock the kitchen with healthier fare. They also provided participants with a treadmill or stationary bicycle for home use, and a pedometer for brisk walking outside. They restricted TV use to one communal room of the home, and attached a timer to the TV to limit the daily time spent watching TV. Finally, the investigators gave the participants a digital body weight scale and encouraged them to self-weigh daily. In conjunction with weekly counseling sessions for the first 6 months, all participants in the home environment-focused intervention lost significant weight at 6 months; the women participants maintained the weight loss at 18 months. What is particularly exciting is that the partners of the study participants all lost and maintained significantly more weight loss, male or female, than partners in the more traditional behavioral weight loss arm, even though they were not the primary targets of the intervention.⁴⁶ Most of these environmental changes are home environment intervention features in our on-going research.⁵³ Several innovations to the foregoing home environment intervention approach need to be noted that will be incorporated in the current intervention design. One difference is that the current proposal features two coaching sessions that actually take place in the home, so that the health coach together with the patient can scan food products in the pantry and the refrigerator and designate each food product as a red light food (limit to no more than once a month), green light food (an everyday food), or yellow light food (nutritiously intermediate food – limit to once a week).⁵⁴ Our community advisory board approved the home visits and our community health workers have been warmly welcomed into participants' homes. The second difference is that our intervention does not seek to ban less healthful choices from the home but instead to position the healthier choices so that they are the most conspicuous and the easiest choice. The literature on behavioral economics suggests that changing the "decision architecture" around the home will be enough to alter food choices; bans are not necessary.^{55,56} We avoided bans because bans can be seen as taking away legitimate choices and lead to pushback by other household members. We also avoided bans because some low-income families have doubled up with other families to share a single apartment and therefore do not have the latitude to ban legitimate food choices.

A third feature is the inclusion of taste-testing as a way to enlarge participants' repertoire of palatable fruits and vegetables. Persistent efforts by nutrition professionals to induce study participants to eat more fruits and vegetables consistently increases participants' liking for and consumption of a greater range of fruits and vegetables.^{25,57-60} Absent the availability of consistent access to nutrition professionals, however, a more practical approach is needed to engender increased liking for a greater variety of fruits and vegetables. The taste-testing will mimic the "product-demonstration" food sampling techniques that food manufacturers use to gain population acceptance of new food products. The taste-testing to be incorporated in the current intervention will consist of fruit and vegetable-rich dishes cooked by a Master's Level nutrition specialist from culturally-tailored recipes contributed by study participants or obtained from governmental organizations (Example: Champions for Change, the California Department of Public Health). The taste-testing sessions will be offered to participants in the MyPlate arm during the group education sessions. The study Intervention Director will conduct nutritional analyses of the recipes for each taste-testing and select the 2 recipes to be presented during the group education sessions that are richest in minimally processed fruits and vegetables, while minimizing sodium. For this study, the two selected recipes were: 1) Vegetable Ceviche

Patterned after protocol published online in association with Appel et al. (2011)¹⁵

and 2) Whole-grain vegetable rich tortas. The selected recipes feature fruits and vegetables that patients most likely have not tasted before in these dishes. The principle behind taste-testing fruit and vegetable dishes that participants have not tasted before is that it can take up to 8-12 exposures (i.e. “tastings”) for humans to like eating a novel plant-based food.^{61,62} Participants will be encouraged to do their own taste-testing experiments with new plant foods, minimally processed, modeling their experiments after the examples prepared for the taste-testing events. Once acquired, liking for a new plant food is unlikely to be lost, absent a change in physiology occasioned by pregnancy or disease.^{63,64} Increased liking for plant-based foods, in turn, should facilitate adherence to the MyPlate recommendation that one half of the typical meal plate be occupied by fruits and vegetables.⁶⁵

